Approximately 7 days after the last retrieval-extinction session, we will test participants' responses to alcohol cues using two Pavlovian procedures, renewal and reinstatement, that have previously been used in studies of laboratory animals to differentiate the effects of retrieval-extinction from extinction alone (Luo et al., 2015). At this visit, participants will return their smartphones.

Each participant will receive a follow-up phone call approximately 30 days after his or her last visit.

The study will take each participant approximately 3 months to complete, depending on how close together sessions can be scheduled. Each type of session is described in more detail in the Study Procedures section.

2. Study procedures

Study Timeline

Session	Beverage	Empty Packaging	Cue Script	Drinking
2-5. Retrieval	X	X	-	X
2-5. Extinction	X	X	X	-
6. Renewal, same room	X	X	X	-
6. Renewal, different room	X	X	X	-
6. Reinstatement, same room	X	-	-	X

Experimental groups and randomization

As we mentioned above, we needed to limit the number of groups for practical reasons. Participants will be randomized to one of three groups: (1) alcohol retrieval / alcohol extinction, (2) soft-drink retrieval / alcohol extinction, and (3) alcohol retrieval / soft-drink extinction. The use of these two control groups (groups 2 and 3) assesses whether the retrieval-extinction procedure requires both its retrieval component and its extinction component. Group 2 represents a traditional CET approach, with

Abbreviated Title: Lab/GMA drinking

Version Date: 2/16/2022

no relevant retrieval procedure. Group 3 controls for mere alcohol exposure in the laboratory, which has actually been shown to have some effect on subsequent drinking (Hodgson & Rankin, 1976; Modell et al., 1993; Pratt & Davidson, 2005).

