Stored biological specimens will be kept in a secure freezer in the Archway's NIDA freezer room until they are analyzed (BRC building; room 01B405). Specimens that are not used up in the analyses will be saved, but will not be used for any purpose not described in the protocol without prior IRB approval.

Urine samples will be kept in a secure freezer in the Archway's NIDA freezer room until they are analyzed (BRC building; room 01B405) and tracked by barcode. Those that are not used up in the analyses will be disposed of after the study. They will not be used for any purpose not described in the protocol without prior IRB approval. Any unplanned loss or destruction of the samples will be reported by the PI to the IRB.

I. Statistical Analysis

1. Outcome measures

Primary: (1) self-reported alcohol craving during the laboratory sessions, (2) GMA reports of alcohol craving and drinking.

Secondary: (1) self-reported alcohol craving and drinking at the 30-day follow-up, (2) heart rate during laboratory sessions and GMA collection periods, and (3) biomarkers for drinking, detected in urine samples collected during laboratory sessions.

2. Analysis of study outcomes

There are two ways in which we are performing multiple tests of statistical significance. First, we have two co-primary outcomes: a lab measure and an ambulatory measure. This design is actually conservative, because we will not consider US retrieval-extinction fully successful if it affects only the first outcome (protection from renewal/reinstatement in a lab setting) without affecting the second outcome (changes in daily-life behavior).

Second, we need to compare our experimental group to each of the two control groups—we expect the control groups to be similar to each other. If the experimental group differs from only one of the control groups, we will have to conclude that the effect of US retrieval-extinction did not actually require both retrieval and extinction, and thus worked via some unexpected mechanism. Although we might ultimately need to perform the two comparisons separately to explore unexpected findings, our main planned analysis is a single test of the joint hypothesis that the experimental group differs simultaneously from both control groups.

Our specific tests will be as follows.

Abbreviated Title: *Lab/GMA drinking*

Version Date: 2/16/2022

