Co-primary outcome 1: Protection from renewal/reinstatement of craving in session 6. We will analyze this in a linear regression model so we can control for a continuous covariate: each participant's mean level of craving in prior sessions (along with any person-level covariates that improve the fit of the model). To test the joint hypothesis that the extinction-retrieval group differs simultaneously from both control groups, we will dummy-code the 3-level predictor Group using two variables: Control Group A (0,1) and Control Group B (0,1), thereby making our intervention group the reference level. We will then perform a Wald test of the joint significance of the two Control Group predictors, maintaining an alpha of .05.

The dependent variable will be operationalized in terms of participants' ratings of alcohol craving in the renewal procedure and the reinstatement procedure from session 6. For each participant, we will generate a summary measure of renewal susceptibility (or, for separate analyses, reinstatement susceptibility) using within-session scores from session 6. For renewal, the score will be calculated as:

(pre-to-post-cue craving change in discordant room) *minus*
 (pre-to-post-cue craving change in concordant room)

For reinstatement, the score will be calculated as:

(pre-to-post-cue craving change after alcohol) *minus*
 (pre-to-post-cue craving change after soft drink)

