Co-primary outcome 2: Reduction of craving and drinking in daily life. This will be analyzed in multilevel models, with the dependent variable operationalized in terms of participants' changes in alcohol craving and alcohol drinking in GMA reports after the four extinction-retrieval sessions, controlling for any preexisting differences. Because we cannot predict the time course of differential changes, our main analyses here will omit GMA data from the period when the four extinction-retrieval sessions are occurring. The dependent variable will be daily frequency of craving reports (or, in a separate analysis, daily number of drinks); the independent variables will be coded the same way as in the models for co-primary outcome 1, with experimental group (3 levels) dummy-coded so the experimental group is the reference level and a Wald test of joint significance can assess whether the experimental group differs simultaneously from both control groups. The continuous covariate will be each participant's overall frequency of craving or drinking during the baseline week of GMA.

Depending on the distribution of the dependent variable, we will use either general linear mixed models (e.g., SAS Proc Mixed) or generalized linear mixed models (e.g., SAS Proc Glimmix or SAS Proc NLMixed)—each of which provides a repeated-measures analysis that can handle missing days or early dropout and can accommodate person-level covariates, which will be included if they improve the fit of the model. These models use maximum-likelihood estimation and allow for specification of an

Abbreviated Title: Lab/GMA drinking

Version Date: 2/16/2022

autoregressive error structure (which can be tested against alternative error structures to provide the best-fitting model). In supplementary analyses, we will examine the time course of any differences that emerge during the period when the four extinction-retrieval sessions are occurring.

Secondary outcomes: Most of the other laboratory measures, such as self-reported craving and drinking at the 30-day follow-up visit, urine biomarkers for drinking, and heart-rate responses to cues, will be analyzed by an ANCOVA approach similar to the one used for the co-primary outcome measure 1. Analysis of the GPS component of the GMA data will be more exploratory, but will include testing for group differences in susceptibility to alcohol craving as a function of nearness to bars and liquor stores—a possible reflection of cue reactivity.

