3. Criteria for significance

Findings will be considered statistically significant at $p \leq .05$, two-tailed, with trends noted at $p \leq .10$.

J. Required Sample Size

We checked prior human studies to find likely effect sizes. For subjective drug craving, the difference between retrieval-extinction participants and control participants had a Cohen d of 1.12 (Xue et al., 2012, figure 3b, change scores for craving on day 4). In a prior human study on reinstatement of physiological reactivity to an extinguished (fear) cue, the difference between retrieval-extinction participants and control participants had a Cohen d of 1.11 (Liu et al., 2014, figure 1). These are large effects. We are powering our study for detection of effects that might be smaller. We used the module “Linear multiple regression: R-squared increase” in G*Power to determine what we could achieve with a realistic sample size. With evaluable data from 75 participants (25 in each of our 3 groups), we will have power of .80 to detect a Cohen f^2 as small as 0.13 on a test of the joint hypothesis that the intervention group differs simultaneously from both control groups in a linear regression model that also contains a covariate for baseline, at a two-tailed alpha of .05. An f^2 of .13 is approximately equivalent to a Cohen d of .61—conventionally considered a medium-sized effect. Despite the large effects seen in the prior studies, we think it is prudent to have power to detect a medium one.

Participants who drop out or are withdrawn from the study will be replaced. We anticipate that we will need to enroll 100 participants in order to have 75 complete the study.

K. Plans for Enrollment at Multiple Sites

Not applicable.

Abbreviated Title: Lab/GMA drinking

Version Date: 2/16/2022

L. Human Subjects Protection Plan

1. The responsibilities of investigators

Responsibilities and qualifications of investigators are given in the protocol appendix.

2. The names of investigators who will obtain informed consent

- [name].
- [name], MSc
- [name].
- [name].
- [name], MS
- [name]
- [name]

Non-FTE staff members will explain the consent form to participants under the direct supervision of a federal employee (FTE) who will sign the consent form.

3. Rationale for subject selection based on gender/ethnic/race categories at risk

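### The planned 2-df Wald test is a global test: it cannot show that the experimental group differs from both controls, and the contrasts that could are left optional

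*Combined protocol and SAP*

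**What the plan says.** Section E.2 (Experimental groups and randomization) explains that using two control groups "assesses whether the retrieval-extinction procedure requires both its retrieval component and its extinction component". Section I.2 follows this through: "If the experimental group differs from only one of the control groups, we will have to conclude" that the effect did not need both components.

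The same paragraph of I.2 then says that "our main planned analysis is a single test of the joint hypothesis that the experimental group differs simultaneously from both control groups". The individual comparisons get a weaker status: "Although we might ultimately need to perform the two comparisons separately to explore unexpected findings".

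For co-primary outcome 1 the experimental group is made the reference level of a linear regression, with one dummy for each control: "We will then perform a Wald test of the joint significance of the two Control Group predictors, maintaining an alpha of .05". For co-primary outcome 2 the same coding is used in multilevel models, where "a Wald test of joint significance can assess whether the experimental group differs simultaneously from both control groups".

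Section J gives power of .80 at f² = .13 with 75 evaluable participants "on a test of the joint hypothesis that the intervention group differs simultaneously from both control groups", and adds: "An f^2 of .13 is approximately equivalent to a Cohen d of .61".

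**The concern.** The joint Wald test has the null hypothesis that the coefficients for control A and control B are both zero. Its alternative is that at least one is non-zero. With three groups this is simply the omnibus group test. It does not depend on which group is the reference, and it has no direction, so choosing the experimental group as reference does not turn it into a test that both controls differ.

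The scientific question needs the stronger statement. If the experimental group beats only the soft-drink-retrieval control, or only the soft-drink-extinction control, the protocol itself says the interpretation changes. The main test cannot separate those cases from the one in which both controls differ. If the conclusion is drawn from the Wald p-value alone, as the plan is worded, a difference from one control would be reported as a difference from both. A reader of Section J would also believe that the claim about both controls has .80 power.

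**Working it through.** **Inputs (Section J).** 75 evaluable participants, 25 per group; one baseline covariate plus two dummies; two-tailed alpha .05; f² = .13; stated power .80. Residual df = 75 − 3 − 1 = 71.

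**1. Reproduce the stated power.** For an R² increase with 2 tested predictors, λ = f² × N = .13 × 75 = 9.75. The noncentral F with 2 and 71 df gives power .787, close to .80 (exactly .80 needs f² = .134). With 1 numerator df the power would be .869. The stated figure therefore belongs to the 2-df global test.

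**2. Express f² as group differences**, in residual SD units with equal groups.
- Both controls differ from the experimental group by d: the means (0, d, d) have variance (2/9)d², so f² = (2/9)d².
- Only one control differs by d: the means (0, 0, d) also have variance (2/9)d².

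The two patterns have the same f², so the Wald test has the same power for each. At f² = .13, d = √(.13 × 4.5) = 0.765. At the protocol's d = .61, f² = (2/9)(.61²) = .083 and the power is .580. The protocol does not show how it converted f² to d.

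**3. Simulate both criteria.** 1,000,000 draws per scenario, 25 per group, 71 df, the two contrasts correlated .5 through the shared reference group. 'Both' means that each contrast exceeds t(.975, 71) in the hypothesised direction.

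| Control A, control B minus experimental (SD) | Wald rejects | Both contrasts significant |
|---|---|---|
| 0, 0 | .050 | .005 |
| .61, 0 | .580 | .023 |
| .765, 0 | .787 | .024 |
| 1.11, 0 | .984 | .025 |
| .4, −.4 | .698 | .0004 |
| .61, .61 | .579 | .405 |
| .765, .765 | .787 | .636 |
| .9, .9 | .907 | .804 |
| 1.12, 1.12 | .985 | .953 |

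**4. Check without simulation.** A single contrast has noncentrality d/√(2/25). This gives power .567 at d = .61 and .760 at d = .765. Power for both contrasts cannot exceed these values, so it must be below .80 at either effect size.

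**5. When both controls truly differ.** The Wald test and both contrasts are significant together in .395 of trials at d = .61 and .628 at d = .765. As a share of Wald rejections that is about 68% and 80%. In the remaining 32% and 20%, a significant Wald result comes without two significant contrasts.

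**6. Completers for 80% power on both contrasts.** About 35 per group (105) at d = .765, or 54 per group (162) at d = .61.

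**The case against.** The best defence is that the plan does not ignore the contrasts. Section I.2 says the experimental group has to be compared with each control and commits to an interpretation if only one differs, which can be applied only by reading the two coefficients. Section I.3 supplies the threshold and Section D the direction. The planned coding prints exactly the two signed contrasts required. On this view the Wald rejections in the table are correct rejections of the global null, and they become false claims only if nobody looks at the coefficients.

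Much of that is right. The 58%, 79% and 70% rejection rates are not error rates of the test, and the harm is conditional. The scenario with controls 0.4 SD either side also departs from the plan's expectation that the controls will be similar. In addition, the fall from .80 to 40% mixes two things. At the same effect size the comparison is .79 against .64 (d = 0.765) or .58 against .40 (d = .61); the rest comes from the f²-to-d conversion, which is a separate matter.

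It does not remove the problem. The paragraph that recognises the one-control case answers it with the single joint test and keeps the separate comparisons for unexpected findings. A significant Wald result would look expected, so nothing would trigger them. No section says that a claim about both controls requires two significant contrasts in the right direction. Step 5 shows why that has to be settled in advance.

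**Conclusion.** The point holds. The test named as the main analysis of both co-primary outcomes does not test the hypothesis it is said to test, and the .80 in Section J belongs to the global test only. For the claim about both controls, power with 75 completers is about 40% at d = .61, 64% at d = 0.765, 80% at d of about 0.90, and 95% at d = 1.12 (the craving effect the protocol takes from a prior study).

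These figures assume 25 per group, equal differences from the two controls and d in residual SD units. They apply to the linear regression of co-primary outcome 1. The logic is the same for the multilevel models of co-primary outcome 2, but their rates were not computed.

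**What to change.** 1. In Sections I.2 and J, describe the Wald test as a global test of any group difference.
2. For each outcome tested this way, make the contrasts of the experimental group with control A and with control B mandatory. Claim a difference from both only if each is significant at two-sided .05 in the hypothesised direction. This is an intersection-union test, so alpha is not split; with one control equal to the experimental group, the false claim rate is at most about 2.5%. Otherwise report both estimates with 95% confidence intervals and do not make the claim.
3. In Section J, attach the .80 to the global test only, and add the power for the claim about both controls at the four effect sizes above. Because those figures are indexed by d, the section should also show its f²-to-d conversion.

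**Cost.** These are text changes; the data and fitted models stay as planned. The downside is a stated power below .80 unless d is about 0.90 or more. Reaching .80 would take 105 completers at d = 0.765 or 162 at d = .61, against the approved ceiling of 75 in Section L.3; no extra enrolment is proposed. Keeping the Wald test as a gate before the contrasts costs about one point of power or less (40.5% to 39.5% at d = .61; 63.6% to 62.8% at d = 0.765).

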We will measure EtG and EtS in urine. If new urine biomarkers for ethanol are discovered while we are running the protocol, we may measure those as well. We will also measure other substances in the urine samples (such as creatinine) that provide quality assurance for the biomarker measurements.

D. Study Objectives

The objective of this study is to test a novel behavioral intervention, US memory retrieval-extinction, for efficacy in attenuating cue-induced alcohol craving and drinking in problem drinkers.

Our co-primary objectives are to determine whether the retrieval-extinction procedure reduces (1) self-reported craving in response to alcohol cues presented in the laboratory and (2) EMA reports of alcohol craving and drinking in daily life. We have designated these as co-primary outcomes because laboratory data are more mechanistically informative and field data are more clinically relevant. We will assess self-reported craving during laboratory sessions conducted within and between four retrieval-extinction sessions, and then in tests for Pavlovian renewal and reinstatement that will follow the final retrieval-extinction session. We will assess changes in EMA reports before, between, and after the laboratory sessions. We hypothesize that, compared to the control groups, individuals receiving alcohol US retrieval-extinction will show reductions in craving (and possibly in drinking) over time. If we detect our hypothesized effects on the EMA measures alone, we will consider that sufficient evidence for the efficacy of the procedure. If we detect our hypothesized effects on the laboratory measures alone, we will consider that suggestive of possible efficacy, indicating that the procedure might need to be administered more intensively in future work.

Abbreviated Title: Lab/GMA drinking

Version Date: 2/16/2022

Our secondary objectives are to test the effects of the retrieval-extinction procedure on (1) self-reported alcohol craving and drinking at the 30-day follow-up by telephone, (2) physiological responses to alcohol cues in the laboratory, and (3) biomarkers for alcohol consumption. We hypothesize that, compared to control groups, individuals receiving US retrieval-extinction will: report less alcohol craving and drinking at the 30-day follow-up telephone contact; have a reduction in physiological responses to cues; and have a reduction in biomarkers for alcohol consumption.

E. Study Design and Methods

1. Study overview

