The session will last approximately one hour. At the beginning and end of the session, participants will rate their alcohol craving using a one-item alcohol craving VAS adapted from that of MacKillop and Lisman (2008): “I want an alcoholic drink right now”; 0 = “I don’t want an alcoholic drink at all,” 100 = “I *really* want an alcoholic drink.” This urge scale will be used to measure craving during the extinction sessions. This same scale will be used for measuring craving during the extinction procedures, renewal test, and reinstatement conducted subsequently (described below). We are using a one-item VAS measure for craving because, in our prior studies, we have usually been better able to detect manipulation effects with these straightforward measures than with multi-item assessments of craving, and there may be good theoretical reasons for that (McGrath, 2005). We will measure craving for soft drinks using a similar VAS except references to alcoholic drinks are replaced by references to soft drinks. The alcohol and soft-drink craving scales are provided in the Appendix.

Before the end-of-session rating, participants will be given a 10-minute period with instructions to initiate progressive muscle relaxation and to focus on deep breathing. The relaxation procedure will be repeated until participants report not feeling stress and craving greater than pre-interview levels. Participants will then be discharged.

Initiation of GMA: During Session 1, participants will each be issued a smartphone. We will show them how to use the phone for EMA entries and ask them to make several practice entries (which will not be used in data analysis). We will explain the automatic collection of location information by the smartphone’s GPS chipset. They will be shown how to charge the phone. They will be asked to keep the phone on and to carry it at all times.

GMA data will be transferred wirelessly from participants’ phones to servers located at the NIDA BRC under a secure communications system developed by the NIDA Biomedical Informatics Section. Transfers will be scheduled to occur automatically at least twice a day. Participants will not have to visit the laboratory for these data transfers. If the remote transfers fail, we can manually initiate a wireless transfer when participants make their regularly scheduled laboratory visits. If that fails, we will swap out the participant’s phone so that the NIDA Biomedical Informatics Section can try to recover the data.

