During extinction, participants will listen to audio recordings of the imagery scripts developed in Session 1. Participants receiving alcohol extinction will listen to their alcohol-related script; participants receiving soft-drink extinction will listen to their alcohol-unrelated script. Participants will also be given their preferred beverage along with empty commercial packaging; these will be the same during extinction as they were during retrieval, but during extinction, participants will not drink.

For all participants, cues will be presented in 5-min blocks: audio imagery scripts for 2 min, beverage exposure for 3 min. Once per min during the 3 min of beverage exposure, the participant will be instructed to take the glass in hand, raise it to his or her nose, and inhale its scent. Participants who drink any of the beverage during the extinction procedure will be discharged from the protocol.

There will be five blocks of cue presentation per session, with 5 min between blocks. In the time between blocks, the cues will be obscured from participants' view. Participants will fill out the one-item alcohol craving VAS if needed and will then be instructed to relax until the next block of cues. The alcohol craving VAS will be given three times during the extinction session: (1) immediately before the first block of cues, (2) immediately after the first block of cues, and (3) immediately after the fifth, final block of cues. The rating taken before the first block will be used to determine whether the beverage itself increased craving (Christiansen et al., 2013; Rose et al., 2014). To check that participants were successfully attending to the cues, following the last urge scale, participants may be asked brief open-

Abbreviated Title: Lab/GMA drinking

Version Date: 2/16/2022

ended questions about the session (e.g., “Tell me about what you did in today’s session...”). Participants will then be allowed to remain in the room and to relax for 20 min, at which point physiological monitoring will be ended, yielding a total extinction time of 65 min. During this period, participants will be given instructions to initiate progressive muscle relaxation and to focus on deep breathing, as after the script generation procedure. If participants are still feeling craving or otherwise “triggered” by the cues at the end of this period, they will receive counseling.

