Finally, participants will be asked to relax in a third, neutral room of the laboratory where their BAC will be checked every 20 minutes until $\leq .01\%$. Participants may be released from the laboratory when their Pre-discharge sobriety test is within normal limits and their BAC is $\leq .01\%$. A copy of the sobriety test is included in the Appendix.

Our decision to use four separate extinction sessions was based on data from previous studies, which showed that by the fourth session of extinction, craving for alcohol had decreased either to the point of not being different from that of neutral-beverage control participants, or by $> 50\%$, or by reaching an asymptote such that additional sessions produced no further consistent declines craving (Blakey & Baker, 1980; Staiger & White, 1991; Staiger et al., 1999; MacKillop & Lisman, 2008). It is possible that US exposure (alcohol drinking for memory retrieval) will itself facilitate extinction (Luo et al., 2015). We believe that it is important to attempt to conduct a sufficient number of extinction sessions to allow the soft-drink retrieval / alcohol extinction group, as well as the alcohol retrieval / alcohol extinction group, to achieve a significant attenuation of cue effects.

c. Session 6: Post-treatment effects of cues in the laboratory

Participants will return their smartphones at the beginning of this visit. They will also complete a timeline follow-back calendar (Sobell et al., 1979; Sobell et al., 1996a) covering the time between Session 5 and Session 6 to provide a retrospective report of “post-extinction” drinking for comparison with that week’s GMA reports.

In the session, all participants will be presented with alcohol cues and an alcohol-containing beverage (i.e., regardless of their previous group assignment to receive only a soft drink or soft-drink cues). Cue-induced craving and physiological changes will be measured in response to two procedures known to enhance responding after Pavlovian extinction procedures (Todd et al., 2014) and to differentiate the effects of extinction with or without prior memory retrieval in laboratory animals (Luo et al., 2015): (1) a renewal procedure, in which the extinguished response may reappear because the CS is presented in a new context and (2) a reinstatement procedure, in which the extinguished response may

Abbreviated Title: Lab/GMA drinking

Version Date: 2/16/2022

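### Co-primary 1 adjusts for craving averaged over prior sessions, most of it rated after the randomised intervention starts, so the adjusted contrast need not be the randomised effect

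*Combined protocol and SAP*

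**What the plan says.** Section I.2, co-primary outcome 1, fits a linear regression to a score computed within Session 6. The predictors are two control-group dummies and each participant's "mean level of craving in prior sessions (along with any person-level covariates that improve the fit of the model". No section limits that mean to ratings made before the intervention.

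Other sections treat the same ratings as outcomes, or as open to treatment:

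- Section I.1 lists as an outcome "Primary: (1) self-reported alcohol craving during the laboratory sessions".
- Section D, under the co-primary objectives: "We will assess self-reported craving during laboratory sessions conducted within and between four retrieval-extinction sessions". It hypothesises reductions in the experimental group relative to the controls.
- Section E.2.b, Extinction: "The rating taken before the first block will be used to determine whether the beverage itself increased craving". The beverage is the randomised element.
- Section E.2.b, on the number of sessions: "It is possible that US exposure (alcohol drinking for memory retrieval) will itself facilitate extinction".

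Two sections point to a baseline covariate instead. Section J obtains its power "in a linear regression model that also contains a covariate for baseline". For co-primary outcome 2, section I.2 adjusts for each participant's "overall frequency of craving or drinking during the baseline week of GMA" and leaves the intervention period out of the main analysis.

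**The concern.** Randomisation protects the comparison of Session 6 scores. It gives no such protection to a comparison made at equal values of something the intervention may already have changed. If craving in Sessions 2-5 differs by group because of the beverage, the cues or faster extinction, and also predicts the Session 6 score, then adjusting for it removes part of a real effect or creates one where none exists. The joint test of the two dummies would then no longer test the total effect of assignment at the stated .05.

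The same sentence admits further covariates according to model fit, with no list or rule. It does not name the two factors by which randomisation is stratified, sex and type of alcoholic beverage.

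**Working it through.** **1. The plan's own figure.** Section J has 75 participants, f² = 0.13, two tested dummies and one covariate. The noncentrality is 0.13 × 75 = 9.75, with 2 and 75 − 4 = 71 df. Power is .787 by noncentral F and .805 by the large-sample Wald version. The stated .80 is reproduced, for a covariate that section J calls baseline.

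**2. What the Session 1-5 mean contains.** Session 1 has two ratings: "At the beginning and end of the session, participants will rate their alcohol craving using a one-item alcohol craving VAS". Each of Sessions 2-5 has one rating before the beverage (section E.2.b, Retrieval) and three during extinction.

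| Ratings | Number | Before any intervention |
|---|---|---|
| Session 1, start and end | 2 | 2 |
| Sessions 2-5, before the beverage | 4 | 1 (Session 2) |
| Sessions 2-5, during extinction | 12 | 0 |
| Total | 18 | 3 |

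So 15 of 18 (83%) follow the first randomised beverage, and 12 follow a randomised beverage in the same session. The moment of randomisation is not stated, but its beverage stratum comes from a Session 1 questionnaire and Sessions 2-5 deliver the assigned condition.

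**3. Formula.** Work in within-group SD units. Let S be a person's underlying craving level, r its correlation with the Session 6 score, ρ the reliability of the covariate, and s the shift in the covariate for a control group relative to the experimental group. The within-group slope on the covariate is r√ρ, so

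adjusted contrast = true contrast − r√ρ × s.

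Example with no true effect, s = −0.5 and r = .3: the false contrast is 0.3 × 0.5 = 0.15 at ρ = 1, and 0.3 × 0.837 × 0.5 = 0.13 at ρ = .7.

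**4. Size under assumed r and s.** The documents give neither, so every row is an illustration. Simulation used 25 per group, the joint 2-df test, 10,000 runs per cell and ρ from .7 to 1.

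Type I error with no true effect and only Control B lower on the covariate:

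| r | Control B 0.5 SD lower | Control B 0.8 SD lower |
|---|---|---|
| 0 | .05 | .05 |
| .1 | .05 | .05-.06 |
| .3 | .07-.08 | .10-.13 |
| .5 | .11-.16 | .21-.31 |

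If both controls shift together by 0.3 to 0.8 SD (ρ = 1), the rejection rate is .06-.12 at r = .3 and .09-.32 at r = .5. With one pre-intervention rating (ρ = .5) it stays at about .05.

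True effect 0.61 SD against both controls (0.61 is the d that section J states), with both controls shifted by 0.5 SD:

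| r | Controls higher: estimate, power | Controls lower: estimate, power | Power, one pre-intervention rating |
|---|---|---|---|
| 0 | 0.61, .55 | 0.61, .55 | .57 |
| .1 | 0.56-0.57, .48-.50 | 0.65-0.66, .61-.63 | .57-.59 |
| .3 | 0.46-0.48, .37-.40 | 0.74-0.76, .75-.79 | .59-.60 |
| .5 | 0.36-0.40, .28-.32 | 0.82-0.86, .88-.94 | .63-.64 |

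Power at 0.61 SD is below .80 even with a sound covariate. With two equal controls, f² = 0.13 corresponds to √(0.13 ÷ (2/9)) = 0.765 SD; that conversion is a separate matter. At 0.765 SD, with controls 0.5 SD higher and r = .3, the estimate is 0.61-0.64 and power .60-.62, against about .80 with one pre-intervention rating.

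**The case against.** - **The correlation may be small.** The Session 6 score is a difference of two within-session changes, so a stable craving level largely cancels. At r = .1 the type I error is at most about .06 in the cells above. This stands as to size. It does not justify the covariate: with r near zero the adjustment gains no precision, and where it does gain precision it can also bias.
- **The direction is not known.** Alcohol-unrelated cues in Control B, or no alcohol before extinction in Control A, could lower prior craving; slower extinction could raise it. This stands, so both directions are shown. Lower control craving would overstate the effect.
- **Little hangs on the laboratory outcome alone.** Section D calls a laboratory-only effect merely suggestive, section I.2 would not call it full success, and co-primary 2 does not use this covariate. This stands and confines the harm to the mechanistic conclusion. That conclusion is still a co-primary result.
- **The wording may just be loose.** Section J's reference to baseline supports that reading. However, section I.2 speaks of sessions in the plural, and only Session 1 lies wholly before the intervention. If baseline was meant, one sentence settles it.
- **Stratification factors and secondary outcomes are separate topics.** This is partly fair. Omitting the strata is mainly a question of precision, but fit-based selection stands in the same sentence and is best corrected with it.

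**Conclusion.** The concern holds: the covariate is wrong as written and should be corrected before analysis. What is certain is the wording, the count of 15 of 18 ratings, the plan's own expectation that these ratings respond to treatment, and the mismatch with section J. What is not known is the size. It rests on the assumed r and shift, and on a simple model in which one underlying craving level links the covariate to the Session 6 score. Under those assumptions the effect runs from nothing at r = 0 to a type I error of about .31 (r = .5, one control shifted by 0.8 SD). The same mechanism can understate or overstate a real effect of 0.61 SD by up to about 0.25 SD (0.5 × 0.5, at ρ = 1). A covariate rated before the intervention removes the problem under every one of these assumptions.

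**What to change.** In section I.2, co-primary outcome 1:

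1. Define the covariate as alcohol craving before any intervention: the start-of-Session-1 rating, or its mean with the Session 2 rating taken before the beverage. Choose one and state it. The mean is preferable for reliability. The end-of-Session-1 rating is less suitable, because the relaxation procedure that precedes it is repeated until craving is back to its level before the interview. Use the same definition in section J.
2. Keep any adjustment for Sessions 2-5 craving as a labelled mediation or sensitivity analysis.
3. In both co-primary models, replace covariates chosen by fit with sex and beverage type.

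For the secondary ANCOVAs, adjust only where a pre-intervention value is collected:

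- **Craving:** the Session 1 Penn Alcohol Craving Scale.
- **Drinking:** the 90-day screening timeline follow-back, or the one covering Session 1 to Session 2. The study overview gives that interval as about 7 days and section E.2.b as 2-3 days; these must be reconciled.
- **Urine biomarkers:** the Session 1 sample.
- **Laboratory heart rate:** no pre-intervention value exists, since monitoring starts after the Session 2 beverage. Analyse it without a post-intervention covariate.

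Cost: wording only, since the ratings are already scheduled. Fewer ratings predict less well. The reduction in standard error is 1 − √(1 − r²ρ). For one rating with ρ = .5 it is about 2% at r = .3 and 6% at r = .5, against 3-5% and 9-13% for a multi-session mean (ρ = .7 to 1). Averaging two such ratings with independent errors gives ρ = 2 × .5 ÷ 1.5 = .67, and reductions of about 3% and 9%. Sex and beverage type use 1 + 2 = 3 df, taking the residual df from 71 to 68.
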